### 9.2.3.2 Exclusion Criteria

Patients receiving a treatment under clinical investigation may not be included in the study.

Previous treatment with an anti-EGFR monoclonal antibody.

## 9.2.4 Matching

Not applicable

## 9.2.5 Baseline Period

Not applicable

## 9.2.6 Study Follow-up

Not applicable

## 9.3 Variables

The following information will be collected:

### Screening

- Informed Consent Signature
- Inclusion and exclusion criteria verification
- Personal data: sex and date of birth.
- Medical history
- Physical examination: weight
- Previous treatment for colorectal cancer
- Primary tumor description: date of diagnosis, TNM stage, surgery, radiotherapy, chemotherapy
- Metastasis: date of diagnosis, metastatic sites, first-line treatment schedule, anti-EGFR

**Baseline**

- Physical examination: ECOG, weight and height
- Prevention of cutaneous toxicity: yes vs no
- Magnesium levels
- Concomitant medications
- AE/SAE
- Administered treatment: administered chemotherapy, administered anti-EGFR and anti-EGFR modifications
- Dermatology Life Quality Index (DLQI) questionnaire
- EORTC QLQ-C30

**Study visit (repetible visit):**

- Physical examination: ECOG, weight and height,
- Prevention of cutaneous toxicity: yes vs no
- Magnesium levels
- Concomitant medications
- AE/SAE
- Skin toxicity/Skin toxicity management
- Administered treatment: administered chemotherapy and chemotherapy modifications, Administered anti-EGFR and anti-EGFR modifications
- Dermatology Life Quality Index (DLQI) questionnaire
- EORTC QLQ-C30

**End Of Study Visit**

To be completed within 28 days (+/- 3 days) after the end of the treatment with anti-EGFR or withdrawal from study for any reason (eg, patient/investigator decision) **or**

**reaching cycle 56:**

- Reason for end of study
- Physical examination: ECOG
- Magnesium levels
- Concomitant medications
- AE/SAE
- Skin toxicity, skin toxicity management
- Dermatology Life Quality Index (DLQI) questionnaire
- EORTC QLQ-C30

Approved

**Study Interruption:**

Reason for study interruption:

- Skin toxicity related to anti-EGFR
- Disease progression- Patient decision
- Investigator decision
- Death

Information available for each subject on all variables will be reported by study site staff in the study-specific sponsor database. The original data source will be patient records, from routine follow-up of subjects.

**Table 1. FLOW-chart**

	Screening	Baseline (Day 1 Cycle 1)	Study visit (repetible visit) Cycle 1-cycle N	End Of Study Visit
ICF signature	x			
Inclusion and exclusion criteria	x			
Personal data	x			
Medical History	x			
Physical examination	x	x	x	x
Disease Information	x			
Prevention of cutaneous toxicity		x	x	
Mg levels		x	x	x
Concomitant Medications		x	x	x
AE/SAE		x	x	x
Skin toxicity and Skin Management			x	x
Treatment administered		x	x	
(DLQI) questionnaire		x	x	x
EORTC QLQ-C30		x	x	x

Approved

### 9.3.1 Exposure Assessment

Treatment adherence: The percentage of delayed cycles, the percentage of cycles administered with reduced doses, the number of administered cycles, the median treatment duration and the average relative dose intensity of anti EGFR drug will be reported.

### 9.3.2 Outcome Assessment

HRQoL will be measured using the EORTC QLQ-C30 questionnaire. The EORTC QLQ-C30 includes 5 functional scales (physical, role, emotional, social, and cognitive functioning), 3 symptom scales (fatigue, pain, and nausea and vomiting), a global health status scale, and a number of single items assessing additional symptoms (dyspnea, sleep disturbances, constipation, and diarrhea), and perceived financial impact. For the majority of the EORTC QLQ-C30 items a 4-point Likert-type response scale is used. The only exception is the global health status/QoL scale in which a 7-point Likert-type scale is used. For ease of interpretation, all scales and individual item responses are linearly converted to a 0 to 100 scale. EORTC QLQ-C30 scores reported during the treatment will be also expressed as percentage of the scores reported at baseline.

Skin satisfaction will be measured using the Dermatology Life Quality Index (DLQI). The DLQI questionnaire includes 10 questions scored from 0 (not at all, not relevant, not answered) to 3 (very much). The DLQI score is calculated by summing the scores of each question resulting in a minimum of 0 and a maximum of 30. A higher score means an impairment of the quality of life. The DLQI score will also be expressed as a percentage of the maximum possible score of 30. DLQI scores reported during the treatment will be also expressed as percentage of the DLQI scores reported at baseline.

Tolerability: The toxicity rate, defined as the percentage of patients, relative to the total of enrolled subjects, experiencing a specific adverse event of any grade, according to National Cancer Institute Common Toxicity Criteria (NCI CTC-AE version 4.02 ), will be reported. Times to onset of dermatological toxicities will be also described.

Treatment adherence: The percentage of delayed cycles, the percentage of cycles administered with reduced doses, the number of administered cycles, the median treatment duration and the average relative dose intensity of every planned drug will be reported.

Management of dermatological toxicity: concomitant medications, both topical and systemic, adopted to prevent or treat dermatological adverse events will be recorded.

Approved

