## 9. Research Methods

### 9.1 Study Design

This is a national, multicentric, prospective, observational trial. The decision to prescribe FOLFOX or FOLFIRI plus panitumumab or FOLFOX or FOLFIRI plus cetuximab must have been freely taken by the clinician prior to the study entry for each patient included. Each physician will see his/her patients within the context of routine visits, without any special visit being organized for the purposes of the study. Therefore, the doctor-patient relationship and patient follow-up are not modified. Physicians are totally free to decide on their patients' therapeutic management.

EORTC QLQ-C30 and DLQI questionnaires will be completed by the patients at baseline (Day 1 of Cycle 1), at the first day of every other cycle (every 2 weeks) thereafter, and at "End of Study Visit" (within 28 days from the end of treatment with anti-EGFR or withdrawal from study for any reason).

Before every cycle, adverse events will be recorded and graded according to NCI CTCAE Version 4.0. Treatment's modifications in terms of cycles' delay, dose reductions or drugs' interruptions will be recorded. Concomitant approaches to prevent or treat dermatological toxicities during the treatment will be registered.

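### Percentage of baseline is undefined at a baseline of 0 and unstable near 0, which matters most for the DLQI, where it is the only baseline-referenced measure the plan names

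*Combined protocol and SAP*

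**What the plan says.** Section 9.3.2 defines two derived outcomes. For the general instrument, "EORTC QLQ-C30 scores reported during the treatment will be also expressed as percentage of the scores reported at baseline". For the skin instrument, "DLQI scores reported during the treatment will be also expressed as percentage of the DLQI scores reported at baseline". Both statements recur in the Abstract (Section 4, outcome variables) and in Section 9.7.2.

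The same section fixes the score ranges. The DLQI has "10 questions scored from 0 (not at all, not relevant, not answered) to 3 (very much"), and the total comes from "summing the scores of each question resulting in a minimum of 0 and a maximum of 30". On direction: "A higher score means an impairment of the quality of life". For the QLQ-C30, "all scales and individual item responses are linearly converted to a 0 to 100 scale". The DLQI is also to be shown as a percentage of its maximum of 30.

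On timing, Section 9.1 says the "questionnaires will be completed by the patients at baseline (Day 1 of Cycle 1"), and Section 9.2.3.2 excludes "Previous treatment with an anti-EGFR monoclonal antibody".

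Section 9.7.2.4 tests the primary endpoint with paired t-tests on mean differences in QoL scores between baseline and follow-up. For the DLQI it names the score itself and t-tests between the two antibody subgroups. Section 9.7.2.1 summarises quantitative variables by mean, SD, median and quartiles. Section 9.7.2.2 rules out imputation, and Section 9.7.2.5 marks sensitivity analysis as not applicable. No section says what happens when the baseline score is 0.

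**The concern.** A ratio to baseline needs a denominator that is never 0 and seldom small. Neither instrument guarantees this. Zero is the best possible DLQI score, and it is a plausible starting value on the first day of treatment in patients never exposed to the drug class that causes the skin toxicity of interest. Items that are not relevant or not answered also score 0, which pulls totals down further.

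The secondary objective in Section 8.2 asks how dermatological adverse events affect skin satisfaction. A patient who moves from no impairment to clear impairment is the plainest example of such an effect, and the ratio cannot record that patient. Among the rest, the size of the percentage depends heavily on where the patient started. The summary would be both selective and hard to interpret.

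**Working it through.** The plan gives no figure for percentage of baseline, so there is nothing of its own to reproduce. The check uses the score ranges in Section 9.3.2.

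**Formula.** Percentage of baseline = 100 × on-treatment score / baseline score.

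**1. Same absolute worsening, different baseline (DLQI).**
- +9 points: 1 to 10 gives 100 × 10/1 = 1000%; 5 to 14 gives 100 × 14/5 = 280%; 0 to 9 is undefined.
- +6 points: from 0, undefined; from 1, 700%; from 2, 400%; from 3, 300%; from 6, 200%; from 12, 150%; from 24, 125%.
- As a percentage of the fixed maximum, +6 points is always 100 × 6/30 = 20 percentage points.

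**2. QLQ-C30 single items.** A 4-point item converted linearly to 0–100 takes the values 0, 33.3, 66.7 and 100. One category upwards is undefined from 0, 200% from 33.3 and 150% from 66.7.

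**3. Patients without a value.** The share at baseline 0 is not in the documents, so the range below is assumed. The bases are the 300 planned patients and the 150 whom Section 9.5 expects to complete the questionnaires throughout treatment.

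| Assumed share at 0 | No value, of 300 | No value, of 150 |
|---|---|---|
| 10% | 30 | 15 |
| 30% | 90 | 45 |
| 50% | 150 | 75 |
| 70% | 210 | 105 |

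**4. What the summary would miss (illustration, all inputs assumed).** Suppose patients at 0 worsen by 8 DLQI points and the others by 2, with non-zero baselines distributed as 1 + Poisson(2).
- Mean change in all patients with 30%, 50% and 70% at 0: 0.3 × 8 + 0.7 × 2 = 3.8; 0.5 × 8 + 0.5 × 2 = 5.0; 0.7 × 8 + 0.3 × 2 = 6.2 points.
- Mean change where the ratio is defined: 2.0 points in every case.
- Mean percentage of baseline: the mean of 1/baseline is (1 − e⁻²)/2 = 0.432, so 100 × (1 + 2 × 0.432) is about 186% in every case. A simulation of 1,000,000 patients agrees.

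The true mean worsening rises from 3.8 to 6.2 points and the ratio summary does not move.

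**5. Weight of small denominators (same assumed baselines, uniform +6 points).** The mean is 100 × (1 + 6 × 0.432), about 359%; the median is 300%. Patients with baseline 1 are about 14% of those with a value (e⁻² = 0.135) and supply about 26% of the total (0.135 × 700/359).

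**The case against.** The strongest reply is that the ratio is a supplementary display. Every statement of it says the scores will *also* be expressed this way, and no test in Section 9.7.2.4 is stated to use it. A patient with a baseline of 0 keeps the raw scores in the planned t-tests and keeps the DLQI as a percentage of 30. For the QLQ-C30, absolute change is already what the primary analysis tests. All of this stands, and it limits the point's weight.

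It does not dispose of the DLQI problem. The paired t-test is written under the primary, QLQ-C30 endpoint. Percentage of 30 only rescales the raw score and makes no reference to where the patient began. That leaves percentage of baseline as the only DLQI measure tied to the patient's own starting point.

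One could also read the ratio as one group mean over another, which would keep patients at 0. The text does not say so, and that reading is unstable too. With the assumed non-zero baselines (mean 3), a uniform 6-point rise would be 100 × (1 + 6/2.1) = 386%, 100 × (1 + 6/1.5) = 500% or 100 × (1 + 6/0.9) = 767% with 30%, 50% or 70% at 0.

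A reader might infer more than the documents support:
- **That the primary analysis is invalid.** It uses scores, not the ratio.
- **That a known, large share of patients is lost.** No baseline distribution is given.
- **That tiny denominators dominate the mean.** In the illustration they inflate it (359% against a median of 300%), and the plan also reports median and quartiles.
- **That 150% is an improvement on some QLQ-C30 scales and a worsening on others, or that 0 on a symptom item means no complaint.** The protocol states neither the directions nor the response labels for that instrument. Absolute change would in any case carry the same ambiguity of direction.

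**Conclusion.** The point holds as a should-fix. Percentage of baseline is undefined at 0 and unstable near it; 0 is attainable on the DLQI and on every QLQ-C30 score; and the plan has no rule for it. This follows from the protocol's own score ranges and needs no assumption.

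The consequence is greatest for the DLQI, where patients who begin unimpaired and then worsen are left out of the only baseline-referenced summary named. For the QLQ-C30 the effect is confined to scales and items on which patients score 0 or close to it at baseline, and the primary paired t-test is untouched.

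The number of patients affected is uncertain: 30 to 210 of 300 across an assumed 10% to 70% at baseline 0. That 0 is a common DLQI starting value is an inference from the timing of baseline and the exclusion of earlier anti-EGFR treatment, not a stated fact.

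**What to change.** - In the Abstract, Section 9.3.2 and Section 9.7.2, replace percentage of baseline with absolute change from baseline in points: 0–30 for the DLQI and 0–100 for each QLQ-C30 scale or item.
- In Section 9.7.2.4, add a paired change from baseline for the DLQI.
- Keep the DLQI as a percentage of 30, which is always defined.
- If the ratio is kept as a display, restrict it to non-zero baselines, summarise it by median and quartiles, and report at each time point how many patients were excluded because their baseline was 0.

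Baseline adjustment and a responder threshold are optional and not needed for this correction; the threshold would require a value that the protocol does not supply.

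The cost is wording in three places and one added DLQI summary, with no new data or patients. The only loss is that the percentage-of-baseline display disappears or is limited.

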### 9.2 Setting and Study Population

#### 9.2.1 Study Period

Around **50** months to enroll 300 patients

Patient's enrollment will start approximately in November 2015 and will end approximately in **December 2019**. The end of study is planned for **December 2020**.

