#### **9.7.2.1 General Considerations**

All recorded parameters will be described: absolute frequency and percentage will be calculated for qualitative variables, while mean, standard deviation, median, first and third quartile will be used to summarize quantitative variables.

The population will be analyzed totally and stratified for treatment (FOLFOX plus panitumumab and FOLFOX plus cetuximab).

The level of significance will be set to  $p < 0.05$ . No interim analyses are planned for this study.

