#### **9.7.2.2 Missing or Incomplete Data and Lost to Follow-up**

There will be no imputation for missing data.

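### Treatment duration, cycle count and time to skin-toxicity onset fall under a plain-summary rule with no censoring or competing-event rule, so mean and upper-quartile duration run low and median onset describes affected patients only

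*Combined protocol and SAP*

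**What the plan says.** Onset is a tolerability item in 9.3.2: "Times to onset of dermatological toxicities will be also described". Section 9.3.1 lists cycle counts and adds that "the median treatment duration and the average relative dose intensity of anti EGFR drug will be reported". No origin, event, censoring rule or estimator is given for either.

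The only summary method is in 9.7.2.1, repeated in the Abstract. It covers all recorded parameters: "mean, standard deviation, median, first and third quartile will be used to summarize quantitative variables". The same section also asks for results by treatment group.

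Observation can end in several ways:
- Section 9.3 fixes the timing of the last assessment: "To be completed within 28 days (+/- 3 days) after the end of the treatment with anti-EGFR or withdrawal from study for any reason". The other trigger named there is "reaching cycle 56".
- Section 9.2.1 adds a calendar limit: "The end of study is planned for" December 2020.
- Section 10.4 keeps data up to withdrawal of consent in the analysis.

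Section 9.7.2.2 says "There will be no imputation for missing data", which does not settle censoring. Sections 9.7.2.5 and 9.7.3 are marked not applicable, and Appendix A lists no stand-alone document that could supply the rule.

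**The concern.** Duration and time to onset are time-to-event quantities, and for some patients observation ends before the event.

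For duration, the event is the end of anti-EGFR treatment. A patient still on treatment at cycle 56, at closure or at withdrawal from the study has a duration known only to exceed the recorded value. A plain summary takes that value as final. The count of administered cycles has the same problem if it is read as the length of a course of treatment.

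For onset, a patient who never has skin toxicity has no onset time, so a plain median is computed in affected patients only. Without that label, a reader may take it as the time by which half of all treated patients are affected.

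At stake is the real-life picture of treatment length and skin toxicity that the study sets out to give. There is also a risk that the by-antibody summaries will be read as a difference in how fast toxicity appears.

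**Working it through.** **Inputs from the documents.** Enrolment runs from November 2015 to December 2019. Counted inclusively that is 50 months, which reproduces the stated window. Closure is December 2020, about 12 months after last entry. The cap is cycle 56. Skin effects occur in 50-90% of patients (section 7) and in more than 90% on panitumumab (7.1).

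**Assumptions.** Entry is uniform, and duration and onset times are exponential. A cycle lasts 2 weeks without delay, although the visit wording in 9.1 is ambiguous. The documents give no expected duration, onset time or withdrawal rate, so ranges are shown.

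**Follow-up window.**
- The cap is 56 × 2 = 112 weeks = 25.8 months. With 1-week cycles it would be 12.9 months.
- The share of the enrolment window that cannot reach cycle 56 before closure is (25.8 − 12)/50 = 27.5%.
- Neither cap nor closure cuts anyone before about 12 months.

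**Duration, cap and closure only.** Let the true median be m and λ = ln 2/m. The share still on treatment when cut is

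c = 0.725·e^(−25.8λ) + 0.275·[e^(−12λ) − e^(−25.8λ)]/(13.8λ).

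The true mean is 1/λ and the plain mean is (1 − c)/λ. For m = 8: c = 0.725 × 0.107 + 0.275 × 0.207 = 0.135, so the plain mean is 11.54 × 0.865 = 10.0.

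Between 12 and 25.8 months the recorded value exceeds t with probability e^(−λt)·[1 − (t − 12)/50]. Setting this to 0.25 or 0.50 gives the plain upper quartile or median.

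| True median (months) | Cut by cap or closure | Plain vs true mean | Plain vs true upper quartile | Plain median |
|---|---|---|---|---|
| 6 | 7% | 8.0 vs 8.7 | 12.0 vs 12.0 | 6.0 |
| 8 | 13% | 10.0 vs 11.5 | 15.2 vs 16.0 | 8.0 |
| 12 | 26% | 12.8 vs 17.3 | 20.7 vs 24.0 | 12.0 |
| 15 | 34% | 14.3 vs 21.6 | 24.0 vs 30.0 | 14.1 |

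A simulation of 300,000 patients agreed to within 0.1 month.

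**Duration, withdrawal while on treatment.** If a share w would leave the study before stopping the drug (at a constant rate), and leaving is counted as stopping, the plain median becomes m(1 − w) as long as that is below 12 months. For m = 8 and w = 10%, 20%, 30% it is 7.2, 6.4 and 5.6 months.

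**Onset.** If a share P of all patients is ever affected, the median among affected patients is the P/2 quantile of the all-patient curve. For P from 50% to 90% that is the 25th to the 45th percentile, whatever the distribution. With exponential times, the all-patient (cumulative incidence) median divided by the plain median is −ln(1 − 0.5/P)/ln 2:
- P = 90%: 1.17
- P = 80%: 1.42
- P = 70%: 1.81
- P = 60%: 2.58
- P = 50%: the all-patient median is not reached

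For scale, assume median onset of 4 weeks in susceptible patients and median treatment of 8 months. The plain median is 3.6 weeks regardless of the susceptible share. The cumulative-incidence median is 5.0 weeks if 90% are susceptible (81% observed affected), 8.2 weeks if 70% are (63% observed), and not reached if 50% are. In the simulation (onset medians of 2 to 8 weeks), cap and closure removed fewer than 0.02% of onsets.

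**Between antibodies.** Take the same onset rate (median 3 months) with median treatment of 4 versus 12 months.
- Plain medians: 3 × 4/7 = 1.7 and 3 × 12/15 = 2.4 months.
- Cumulative-incidence medians, with P = 4/7 and 0.80: 5.1 and 3.4 months.

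Both depend on time on treatment, in opposite directions.

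**The case against.** These are secondary descriptive items, and 7.3 says the analyses are descriptive only. The duration summary named in the exposure and outcome sections is the median, which cap and closure leave intact up to about 12 months. The plan does not rule out a Kaplan-Meier median, so the bias is inferred from its silence. The median onset among affected patients is a legitimate quantity, and 9.3.2 places it directly after a toxicity rate whose denominator is all enrolled patients. At the frequency stated for panitumumab the gap is small.

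Most of this stands and limits the point. What remains is that 9.7.2.1 requires mean and quartiles for every quantitative variable, on-treatment withdrawal can move even the median, and nothing requires the onset denominator to be stated.

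Four stronger readings are tempting but not supported:
- *Both variables are reported too short.* Not for median duration, apart from the two exceptions above. For onset, the affected-only median answers a different question and is not in itself an error.
- *Early stopping of anti-EGFR biases duration.* Stopping is the event being timed, so that value is complete.
- *The longest-treated patients lose their final questionnaires.* Reaching cycle 56 is an explicit End Of Study trigger. Patients on treatment at closure complete both questionnaires at study visits, and the withdrawal clause might be read to cover them.
- *Cumulative incidence makes the antibodies comparable on onset.* The last calculation shows that it does not.

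**Conclusion.** The point holds in limited form. Taken literally, the plan treats cut durations and cycle counts as complete. The mean duration is then low by about 0.6 months at a true median of 6 (8.7 − 8.0, before rounding), 1.5 at 8 and 4.5 at 12. The upper quartile is low once it passes about 12 months. Median duration is safe unless patients withdraw while on treatment or the true median exceeds about 12 months.

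For onset, the plain median is an affected-patients figure. It is about 15% below the all-patient median when 90% are affected (1/1.17 = 0.85), and has no all-patient counterpart near 50%.

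The sizes rest on exponential times, uniform entry, 2-week cycles and closure in December 2020. The Milestones section gives the end of data collection as the first quarter of 2021. If patients were followed to March 2021, the 12-month threshold would become about 15 months. The direction of the duration bias and the P/2 percentile result do not depend on the exponential assumption.

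The change is worth making because the better methods are standard and the dates they need come with data the study already records.

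**What to change.** In 9.7.2.1 and 9.7.2.4, exempt these time variables from the plain-summary rule and define origin, event and censoring for each.

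- **Treatment duration:** Kaplan-Meier with 95% CI. The event is end of anti-EGFR; censor at withdrawal while on treatment, at cycle 56 and at study closure. Give no unqualified mean. State beside any cycle-count summary how many patients were cut at each limit.
- **Skin-toxicity onset:** a cumulative incidence curve over all treated patients (Aalen-Johansen), with end of anti-EGFR or death as competing events. Label any median as being among affected patients and show it with the toxicity rate.
- **Between antibodies:** state that differences in onset medians, by either method, are not to be read as differences in onset rate, because both depend on time on treatment.
- **Data collection (9.3):** record study closure and reaching cycle 56 as reasons for end of study, so that censored durations can be identified. The interruption reasons now listed include neither.

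The cost is a few lines of text, two reason codes and routine procedures. The downside is that upper quartiles of duration, or a cumulative-incidence median, may be imprecise or not reached.
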